6.8.2. Allowed Concomitant Therapy and Rescue Therapy

If medically necessary due to intolerable symptoms, rescue therapy will be permitted at the discretion of the investigator based on disease worsening as evaluated by the investigator (ie, increased EASI or BSA), or as reported by the subject (ie, worse itch). Optimized skin care is expected to be followed prior to and maintained throughout the study as per current guidelines and recommendations for AD (eg, avoidance of irritants).

Whenever possible during the Double-Blind Treatment Period, rescue therapies should be withheld for at least 4 weeks from the start of the study treatment. If possible, investigators should attempt to limit initial rescue therapy to topical medications as a first line treatment for AD and AD flares according to current guidelines and recommendations (Eichenfield 2014, Eichenfield 2017). Primarily topical medium potency corticosteroids such as triamcinolone acetonide 0.1% and fluocinolone acetonide 0.025% should be used, and applied to problem areas only, in conjunction with oral antihistamines, if needed. Topical calcineurin inhibitors may also be applied to problem areas if additional therapy is required for intractable symptoms. Only when symptoms continue to persist are systemic corticosteroids or nonsteroidal systemic immunosuppressive drugs (eg, cyclosporine, methotrexate, mycophenolate mofetil, azathioprine) recommended for rescue therapy.

If a subject receives rescue therapy with systemic corticosteroids or non-steroidal systemic immunosuppressive drugs, study treatment will need to be immediately discontinued. After treatment with these medications is completed, study treatment may be resumed if deemed appropriate by the investigator and the medical monitor, but no sooner than 5 half-lives after the last dose of systemic rescue medication.

Rescue therapies and the indication and details (ie, name, dose, frequency of administration, strength, duration of use) will be recorded in the subject's chart and eCRF, if applicable. Investigators should make every attempt to conduct efficacy and safety assessments (eg, disease severity scores, safety labs) immediately before administering any rescue treatment. An unscheduled visit may be used for this purpose, if necessary.

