11.4.2. Sensitivity Analyses

In addition to the primary methods for handling missing data and rescue medication use in the FAS described in Section 11.4.1, the following sensitivity analyses will be performed for the primary and key secondary endpoints using alternative methods to handle missing data and rescue medication use, and/or in alternative analysis populations:

- For the MI analysis of percentage of change in EASI from Baseline to Week 12, data missing at random within each treatment group will be investigated using tipping point analysis method ([REDACTED]).
- Percentage of change in EASI from Baseline to Week 12 will be analyzed in the modified Full Analysis Set (mFAS), data will be set to missing after rescue medication uses; all missing data will be imputed using post-baseline last observation carried forward method.

- Percentage of change in EASI from Baseline to Week 12 will be analyzed in the mFAS set, data will be set to missing after rescue medication uses; all missing data will be imputed using post-baseline worst-case-carry-forward method.
- Proportion of subjects achieved EASI-75 response at Week 12 will be analyzed in the mFAS set using EASI scores imputed by the MI method discussed in Section 11.4.1.
- Observed data analyses in mFAS set, regardless of rescue medication uses and without missing data imputation:
 - For longitudinal continuous variables (eg, percentage of change in EASI from Baseline to Week 12), mixed effects model with repeated measures (MMRM) analysis will be performed and by visit results will be reported;
 - For longitudinal dichotomous measures (eg, EASI-75, vIGA 0 to 1), logistic regression analysis will be performed by visit.
- Completers analyses of primary and secondary endpoints for subjects who complete 12 weeks of study treatment.
- Analyses of primary and key secondary endpoints in the Per Protocol set.

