It is assumed that the percent change in EASI from Baseline to Week 12 will be normally distributed with an estimated standard deviation (SD) of 41%. Assuming a 1:1:1 randomization, 120 subjects (40 subjects each in 1 mg etrasimod, 2 mg etrasimod, and placebo groups) is sufficient to achieve at least 90% power to detect a difference of 35% in EASI from Baseline to Week 12 between each of the etrasimod treatment groups and placebo by a 2-sample t-test using a 1-sided significance level of 0.025. This sample size also accounts for an estimated drop-out rate up to 25%.

D. Treatment Randomization

Randomization will be stratified by vIGA score at Baseline (3 versus 4) and region

E. Assessment Schedule

For the statistical analysis, DB Treatment Period will include 12 weeks treatment and 4 weeks safety follow-up; OLE Period will include 52 weeks treatment and 4 weeks safety follow-up. The date at which the subject is randomized will be referred to as the “Baseline/Day 1”. Subjects will be requested to attend the following scheduled visits for the DB Treatment Period from their Baseline/Day 1 visit: Week 1, 2, 4, 6, 8, 12 and Week 16/SFU visit. For the OLE Period, Week 16 (this will be same as Week 16 in the DB Treatment Period), Week 17, 18, 20, 24, 28, 32, 40, 48, 56, 68, and Week 72/ SFU. The acceptable visit window for scheduled visits for the DB Treatment Period including Week 16, and Week 17 and 18 in OLE Period is ± 3 days, for all the other OLE visits, the scheduled visit window is ± 7 days. Visits that subjects make to the clinic outside the visit window are recorded as unscheduled visits.

Please refer to protocol for details.

5. General Analytical Considerations

A. Data Sources and General Rules

Data are recorded on electronic case report form (eCRF) for each subject screened/enrolled in this study. These forms will be used to transmit information collected during the study to the Sponsor and regulatory authorities, as applicable. Laboratory data, [REDACTED] blood samples and [REDACTED] data are collected separately by the selected vendors. Section 14 of the protocol provides additional details regarding data handling and record keeping.

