Modified Full Analysis Set (mFAS)	The mFAS consists of all randomized subjects who received at least 1 dose of study treatment, have a baseline measurement, and have at least 1 post-randomization measurement. The mFAS is endpoint specific, therefore subjects included in the analysis set for 1 endpoint may differ from another endpoint, based on the baseline and post-baseline data.
Per Protocol Set (PPS)	The PPS consists of all subjects in the FAS who adhere to the protocol. The PPS will be used in sensitivity analyses of the primary and key secondary endpoints to evaluate the influence of major protocol violators and protocol deviators on the primary results. Specific reasons for warranting exclusion from this analysis set will be documented prior to database lock and may include, but are not limited to: 
 • Not meeting critical inclusion/exclusion criteria • Study treatment noncompliance • Receiving incorrect study treatment • Missing more than a defined number of visits while still on study • Chronic prohibited medication use while on study treatment
Treatment Completer Set (TCS)	The TCS includes subjects in EASI or vIGA specific mFAS who have completed 12 weeks of study treatment in DB Treatment Period.
Safety Set (SAF)	The SAF includes all randomized subjects who received at least 1 dose of study treatment.
[REDACTED]	[REDACTED]
Post Hoc Analyses Set (PHAS)	The PHAS excludes 9 subjects from the Full Analyses Set in the 2 mg treatment group with unwarranted dose interruption due to lymphocyte decrease between week 4 and 12
OLE Period	
OLE Safety Set (OLE SAF)	The OLE SAF includes all subjects who enrolled in the OLE Period and received at least one dose of etrasimod. All safety

	
and efficacy analysis in the OLE Period will be performed over OLE SAF. For the analyses of efficacy endpoints, subjects will further be required to have at least one efficacy measurement in the OLE Period. Therefore, efficacy evaluable set is endpoint specific.

H. Missing Data

In order to analyze primary and secondary efficacy endpoints at Week 12 in the FAS, the handling of missing data and rescue medication uses are specified in Section 8.B - 8.C. No imputation will be implemented for exploratory efficacy and safety endpoints. The handling of missing reporting information for safety assessments are specified in Section 9.

I. Data Display Characteristics

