EASI values at scheduled visits up to Week 12 will be analyzed using a MMRM model. The MMRM model will include treatment group, visit, and interaction of treatment-by-visit as factors, baseline EASI and baseline vIGA (3 versus 4) and region [REDACTED] as covariates. An unstructured (UN) covariance matrix will be specified for the MMRM model. If the model does not converge using an unstructured covariance matrix, an auto-regressive AR(1) structure will be tested. If AR(1) fails to converge, a compound symmetric structure will be used. LS means and LS mean differences at each visit between treatment groups with p-values and corresponding 95% CIs will be reported.

The same ANCOVA model as described above for the primary analysis will be performed, using the following:

- Last Observation Carried Forward (LOCF): The primary endpoint will be analyzed in the modified FAS (mFAS), with assessments after the first use of rescue medication set to missing. All missing data will be imputed using post-baseline LOCF method.
- Worst Case Carried Forward (WCCF): The primary endpoint will be analyzed in the mFAS, with assessments after the first use of rescue medication set to missing. All missing data will be imputed using post-baseline WCRF method.
- Observed Cases (OC) in mFAS: observed data analyses in mFAS, regardless of rescue medication uses and without missing data imputation,

will be performed using a mixed effects model with repeated measures (MMRM) including all scheduled visits up to Week 12.

- OC in Per Protocol Set (PPS): observed data analysis will be performed among PPS, regardless of rescue medication uses and without missing data imputation.
- OC in treatment completers (TCS): observed data analysis will be performed among mFAS subjects who have completed 12 weeks of study treatment, regardless of rescue medication uses and without missing data imputation.

C. Key Secondary Efficacy Outcome Analyses

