
 Percent change in EASI from Baseline to Week 12 	
 FAS, MI (ANCOVA) 	
 #1 FAS, MI tipping point analysis (ANCOVA) #2 mFAS, MI (ANCOVA) #3 mFAS, LOCF (ANCOVA) #4 mFAS, WCCF (ANCOVA) #5 mFAS, OC (MMRM) #6 PPS, OC (ANCOVA) #7 TCS, OC (ANCOVA)
Key Secondary		

 EASI-75 at Week 12 vIGA response at Week 12 	
 FAS, NRI (CMH) 	
 #1 FAS, MI (CMH), (EASI-75 only) #2 mFAS, NRI (CMH) #3 mFAS, OC (Logistic regression) #4 PPS, OC (CMH) #5 TCS, OC (CMH)
Other Secondary		

 Percent change in peak pruritus NRS from diary from Baseline to Week 12. Change and percentage change in percent BSA (total and 8 body regions) from Baseline to Week 12 (no sensitivity analysis for individual body regions). 	
 FAS, OC (MMRM) 	
 #1 PPS, OC (MMRM) #2 TCS, OC (MMRM)

 Peak pruritus NRS ≥ 3 reduction from Baseline to Week 12. EASI-50 at Week 12. EASI-90 at Week 12. 	
 FAS, NRI (CMH) 	
 #1 PPS, OC (CMH) #2 TCS, OC (CMH)
Exploratory		

 Change in DLQI from Baseline to Week 12. Change in POEM from Baseline to Week 12. Percent change in SCORAD (total, 6 severity/intensity symptoms, and 2 subjective 	
 FAS, OC (MMRM) 	N/A

symptoms) from Baseline to Week 12. [REDACTED]		
[REDACTED]	[REDACTED]	N/A
[REDACTED]	[REDACTED]	N/A
OLE Period		

 • EASI • vIGA • SCORAD • NRS • BSA • DLQI • POEM • PGA 	
 • OLE SAF, OC 	N/A

DB=Double Blind; OLE=Open-Label Extension.
 FAS=Full Analysis Set; mFAS=modified Full Analysis Set; PPS=Per Protocol Set; TCS=Treatment Completer Set; SAF=Safety Analysis Set.
 MI=Multiple Imputation; NRI=non-responder imputation; LOCF =Last Observation Carried Forward; WCCF=Worst Case Carried Forward; OC= Observed Case.
 EASI=Eczema Area and Severity Index; vIGA= validated Investigator’s Global Assessment; DLQI= Dermatology Life Quality Index; POEM= Patient-Oriented Eczema Measure; SCORAD= SCORing Atopic Dermatitis; PGA= Patient Global Assessment.

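### The per-protocol analyses of percent change in EASI, EASI-75 and vIGA change rescue and missing-data handling along with the population, so they cannot cleanly show what protocol deviators did to the primary results

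*SAP*

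**What the plan says.** **Primary and key secondary rules.** Under SAP 8.B, percent change in EASI is analysed in the Full Analysis Set (FAS). EASI after rescue is set to missing, missing values are multiply imputed (MI), and the model is ANCOVA. Under SAP 8.C, EASI-75 and vIGA response are analysed in the FAS by CMH, with missing and post-rescue status counted as non-response (NRI).

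**PPS and TCS rules.** For percent change in EASI, SAP 8.B says "OC in Per Protocol Set (PPS): observed data analysis will be performed among PPS, regardless of rescue medication uses and without missing data imputation". The TCS bullet applies the same two conditions. SAP 8.C runs both sets on OC for EASI-75 and vIGA, and defines OC in that section as ignoring rescue and not imputing. Table 3 agrees, and lists no PPS or TCS row with MI or NRI for these endpoints.

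**Purpose.** SAP Table 2 and Protocol Table 7 say the PPS serves "to evaluate the influence of major protocol violators and protocol deviators on the primary results". No such purpose is stated for the TCS.

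**Rescue.** Protocol 6.8.2 says "rescue therapy will be permitted at the discretion of the investigator", with topical treatment first. It requires study treatment to stop for systemic corticosteroid or systemic immunosuppressant rescue, and states no such requirement for topical rescue.

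**Protocol list of sensitivity analyses.** Protocol 11.4.2 has a bullet headed "Observed data analyses in mFAS set, regardless of rescue medication uses and without missing data imputation". The completer and Per Protocol analyses are separate bullets that give no rescue or missing-data rule.

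**The concern.** To learn how deviators influence a result, one removes them and leaves everything else alone. Here a subject treated with topical corticosteroid under 6.8.2 is a failure in the main EASI-75 analysis. If that subject stays in the PPS or TCS and clears, the same subject becomes a responder for the assigned arm. The study objective concerns etrasimod monotherapy, so this is a different question from the one the primary analysis asks.

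At stake is how the PPS tables will be read. A gap between PPS and primary results could come from deviators, from steroid effect, or from dropping missing data. Agreement is also weaker reassurance than it looks, because these influences can offset one another.

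**Working it through.** **1. The plan's own reference figure.** SAP 4.C assumes a 35-point difference ("detect a difference of 35% in EASI from Baseline to Week 12"), an SD of 41, a "1-sided significance level of 0.025" and up to 25% drop-out, and states that 120 subjects are "sufficient to achieve at least 90% power". A two-sample t-test with 30 evaluable per arm gives power 0.902, and 30/(1 − 0.25) = 40 per arm, or 120 in all. The figure reproduces and is not disputed; 35 points is used below only as a yardstick.

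**2. The listed analyses side by side.**

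| Endpoint | Set | Post-rescue data | Missing data | Method |
|---|---|---|---|---|
| % change EASI (primary) | FAS | set to missing | MI | ANCOVA |
| % change EASI | mFAS | MI row in Table 3 | MI | ANCOVA |
| % change EASI | mFAS | kept | not imputed | MMRM |
| % change EASI | PPS, TCS | kept | not imputed | ANCOVA |
| EASI-75, vIGA (main) | FAS | non-response | non-response | CMH |
| EASI-75, vIGA | mFAS | NRI row in Table 3 | non-response | CMH |
| EASI-75, vIGA | mFAS | kept | not imputed | logistic |
| EASI-75, vIGA | PPS, TCS | kept | not imputed | CMH |

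For the modified FAS (mFAS), Table 3 has rows that keep the main missing-data method and change the set. For these endpoints no pair of rows differs only in FAS or mFAS versus PPS or TCS.

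**3. Benchmark.** If no deviator is removed and the primary rules are kept, the shift is exactly 0. Any shift found below, also with no deviator removed, is due to the switch to OC alone. These are expected values, not simulations.

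**4. Percent change in EASI.** The documents give no rescue rates and no size for the rescue effect. Assume MI recovers the 35-point difference, topical rescue adds g points of improvement in either arm, and fractions r_P (placebo) and r_E (etrasimod) are rescued. Then

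OC difference = 35 − g × (r_P − r_E).

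- g = 20, 30% v 10%: 35 − 20 × 0.20 = 31
- g = 40, 30% v 10%: 35 − 40 × 0.20 = 27
- g = 40, 40% v 10%: 35 − 40 × 0.30 = 23
- g = 20 or 40, 10% v 30%: 35 + 4 = 39 or 35 + 8 = 43
- equal rates: 35

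The shift runs from −12 to +8 points.

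**5. EASI-75.** Assume unrescued response p of 50% (etrasimod) and 20% (placebo), response after rescue q in either arm, rescued fraction r and missing fraction m:

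NRI rate = (1 − r − m) × p; OC rate = [(1 − r − m) × p + r × q] / (1 − m).

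- m = 0, rescue 30% placebo v 10% etrasimod. NRI: 0.90 × 0.50 − 0.70 × 0.20 = 0.45 − 0.14 = 31 points. OC with q = 20%, 40%, 60%: 27, 23, 19 points.
- m = 25%, rescue 20% in both arms. NRI: 0.55 × 0.50 − 0.55 × 0.20 = 16.5 points. OC: 16.5/0.75 = 22.0 points, whatever q is, because the rescue terms cancel.
- m = 25%, rescue 10% placebo v 30% etrasimod, q = 60%. NRI 9.5 points; OC 28.7 points.
- m = 0, rescue 20% in both arms: 24 points under either rule.

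The shift runs from about −12 to +19 points.

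**The case against.** **OC is not forbidden.** A reader might infer that the SAP departs from the protocol without declaring it in SAP Section 11. The documents do not support that. Protocol 11.4.2 introduces these analyses as using alternative methods, alternative populations, or both; it sets no rule for the completer and Per Protocol bullets, and Protocol 11.1 leaves detail to the SAP. The fault is only that OC does not serve the stated PPS purpose.

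**Rescued subjects may not all be in the PPS.** A reader might take it that every rescued subject stays in. This is not established. The exclusion reasons are open-ended, they include chronic use of prohibited medication, and much of the prohibited list in Protocol 6.8.3 is redacted. Some sustained topical-steroid users may be removed. What stands is that permitted topical rescue is not itself a listed exclusion, and the TCS definition contains no medication exclusion.

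**There is a bridge.** The mFAS OC analyses, and the post hoc FAS OC analysis of EASI in SAP 12.C, ignore or may ignore rescue as the PPS rows do, so calling the PPS results uninterpretable would go too far. The bridge is partial: it runs through MMRM rather than ANCOVA for EASI, and through logistic regression rather than CMH for responders.

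**The TCS is different.** Its stated purpose is not to study deviators, an OC analysis of completers is conventional, and little Week 12 data should be missing among them. For the TCS only the rescue handling remains an issue.

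**Consequences are limited.** SAP 5.F and Protocol 11.6 plan no formal testing strategy, and the documents state no decision rule that depends on the PPS or TCS. Where placebo subjects use more rescue, the EASI shift in step 4 is against etrasimod. That direction is not assured: heavier rescue on etrasimod, or dropping missing responders' data, can enlarge the difference.

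**Conclusion.** The concern holds in a limited form. As written, the PPS analyses of percent change in EASI, EASI-75 and vIGA cannot cleanly isolate the influence of deviators, because rescue and missing-data handling change with the population. In the PPS and the TCS, post-rescue scores of any topically rescued subjects who remain count for the assigned arm.

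Size and direction are not known. On the assumed rescue rates (10% to 40% per arm), rescue gains (up to 40 points), response rates and missingness (up to 25%), the rule change alone moves the EASI difference by −12 to +8 points and the EASI-75 difference by about −12 to +19 points. It moves neither when rescue is balanced, its effect is the same in both arms, and no data are missing. A reader might infer that the efficacy conclusion is biased; it is not, since the primary and key secondary analyses already apply their own rescue rules and are untouched. This is an inexpensive improvement to supporting analyses in an exploratory phase 2 trial.

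**What to change.** In SAP 8.B, 8.C and Table 3:

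- **PPS, percent change in EASI:** add an analysis with post-rescue EASI set to missing and the primary ANCOVA, using the imputations fitted in the FAS and then restricted to PPS subjects. Refitting the imputation within the PPS would again change more than the population.
- **PPS, EASI-75 and vIGA:** add a CMH analysis with rescue or missing data counted as non-response.
- **TCS:** add the same rescue handling for the three endpoints.
- **Existing OC rows:** keep them as supplementary, labelled as including rescue effects.

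The cost is SAP wording, a rerun of existing code on two subsets, and a few more tables.

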2. OBJECTIVES

Primary Objective

- To assess the efficacy of etrasimod monotherapy (1 or 2 mg) in subjects with moderate-to-severe AD during the Double-Blind Treatment Period.

Safety Objective

- To assess the safety and tolerability of etrasimod monotherapy (1 or 2 mg) in subjects with moderate-to-severe AD during the Double-Blind Treatment Period.

Open-Label Extension Objective

[figure not shown]
- To assess the long-term safety, tolerability, and efficacy of etrasimod monotherapy (2 mg) in subjects with moderate-to-severe AD.

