The scores from the 7 questions are added up to give an overall POEM score (0-28). An overall POEM score of 0-2 = ‘clear/almost clear’, 3-7 = ‘mild’, 8-16 = ‘moderate’, 17-24 = ‘severe’, and 25-28 = ‘very severe atopic eczema’.

- **DLQI** is a 10-item patient-reported outcome (PRO) measure that assesses the extent to which the skin condition has affected the subject’s quality of life over the past week, including 6 domains (daily activities, personal relationships, symptoms and feelings, leisure, work/school, and treatment). Total score (0-30) will be calculated as the sum of 10 questions with each ranging from 0 to 3. The scoring of each answer is as follows:

Very much	Scored 3
A lot	Scored 2
A little	Scored 1
Not at all	Scored 0
Not relevant	Scored 0
Question unanswered	Scored 0

Question 7	Question 7A	Score
Yes	Any response	3
No	A lot	2
No	A little	1
No	Not at all	0
Not relevant	Any response	0

[figure not shown]
If one question is left unanswered this is scored 0 and the scores are summed and expressed as usual out of a maximum of 30. If two or more questions are left unanswered the total DLQI score is missing. If question 7 is answered ‘yes’ or ‘not relevant’, then the answer of 7a will be ignored.

B. Primary Efficacy Outcome Analysis

The primary endpoint of percentage change in EASI from Baseline to Week 12 will be analyzed based on the FAS using an analysis of covariance (ANCOVA) model. The ANCOVA model will include treatment group as factors, Baseline EASI score and the two randomization factors of baseline vIGA (3 versus 4) and

region [REDACTED] as covariates. EASI scores after rescue medication use will be set to missing. All missing EASI scores at scheduled visits up to Week 12 will be imputed using a multiple imputation (MI) technique with a fully conditional specification (FCS) method and predictive mean matching (PMM) for EASI scores (Heitjan 1991, van Buuren 2007). The rescue medications considered for the purposes of efficacy analysis will include topical and systemic corticosteroids used during the DB Treatment Period of the study.

For MI, 100 imputation models will be generated, including treatment, baseline vIGA (3 versus 4), region [REDACTED] baseline EASI score, and EASI scores at the previous scheduled visits. Percent change in EASI at Week 12 will be derived from the imputed EASI values.

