Multiple results of ANCOVA (least square [LS] means and LS mean difference between etrasimod and placebo) for each MI dataset will be combined and reported along with 95% CI and p-value and using Rubin's method ([REDACTED]).

All subjects are required to have a baseline EASI score upon randomization. In the unlikely event that a subject is missing baseline EASI, the baseline value will be imputed first using the above covariates. The imputation model will be modified as appropriate based on the actual data.

In addition to the primary method for handling missing data and rescue medication use in the FAS, the following sensitivity analyses will be performed using alternative methods and/or in alternative analysis set:

- FAS, MI tipping point analysis

A tipping point analysis (Carpenter and Kenward 2013) will be performed to investigate the robustness of departures from the missing at random (MAR) assumption in the MI model by applying a specified sequence of shift parameters that modify the imputed EASI values, as follows:

- Missing EASI values will be imputed 100 times, following the MI method described above, with adjustment to the imputed EASI by shift

parameter $S_1=0.5$ in both etrasimod groups. A positive adjustment assumes a worsened outcome. The adjusted EASI value will be capped at 72. Imputed percent change in EASI will be derived accordingly. The MNAR statement with the ADJUST option in PROC MI will be used to apply the shift parameter.

- Each of the 100 completed datasets applying the shift parameters will be analyzed using an ANCOVA model as described above. The results from the 100 completed datasets will be combined for inference using PROC MIANALYZE.
- Repeat the above steps, with adjustment by shift parameter $S_2=1.0$ in both etrasimod groups. Repeat the process for the following pre-specified shift parameters: 0.5, 1.0, 1.5, 2.0...71.5, 72
- The shift parameters that result in a reversed study conclusion (i.e., p-value increases from <0.05 to ≥ 0.05) will be indicated.
- mFAS, using OC (observed data regardless of rescue medication uses and without imputation)

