The two proportion-based key secondary endpoints (EASI-75 at Week 12 and vIGA response status at Week 12) will be analyzed in the FAS using the Cochran-Mantel-Haenszel method (CMH) adjusted for randomization stratification factors of baseline vIGA score (3 versus 4) and region [REDACTED]. Missing data will be imputed in the FAS using the NRI method: missing dichotomous response status at Week 12 (including those after use of rescue medication) will be imputed using the non-responder imputation (NRI) method, ie, “non-responders” or “failure” for missing response. The number, percentage of subjects achieving the goal and Clopper-Pearson exact 95% confidence intervals will be reported. The differences in proportion between treatment groups, along with p-values and the 95% CIs will also be reported.

The following sensitivity analyses will be performed:

- FAS, MI

Missing Week 12 EASI-75 response status will be derived based on the multiple imputed datasets for EASI values as described above. The same CMH test will then be performed for EASI-75 and combined using Rubin’s method. Combined proportion along with the 95% CI, and p-value will be reported.

- mFAS, using OC (observed data regardless of rescue medication uses and without imputation)

Response endpoint at Week 12 will be analyzed using a logistic regression model including treatment group as factor, Baseline EASI score and the two randomization factors of baseline vIGA (3 versus 4) and region [REDACTED] as covariates. Odds ratio of etrasimod versus placebo along with the p-value and 95% CI will be reported.

The same CMH test as described above will be performed for the key secondary endpoints, using the following:

- PPS, using OC
- TCS, using OC

D. Other Secondary Efficacy Outcome Analyses

Secondary efficacy endpoints will be analyzed using the below methods:

[figure not shown]

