- Longitudinal continuous variables (percent change in weekly peak pruritus NRS, change and percentage change in %BSA) measured at visits (weeks) up to Week 12 will be analyzed with a MMRM model based on FAS using observed data. The MMRM model will include treatment group, visit (week), and interaction of treatment-by-visit (week) as factors, and baseline measure and randomization stratification factors as covariates. An unstructured covariance matrix will be specified for the MMRM model. If the model does not converge using an unstructured covariance matrix, an auto-regressive AR(1) structure will be tested. If AR(1) fails to converge, a compound symmetric structure will be used. LS means at visit (week) and LS mean differences at visit (week) between treatment group with p-values and corresponding 95% CIs will be reported.
- Dichotomous measures (weekly peak NRS ≥ 3 reduction, EASI-50, and EASI-90) at Week 12 will be analyzed in the same way as for the key secondary endpoints based on FAS with CMH method adjusted for randomization stratification factors of baseline vIGA score (3 versus 4) and region [REDACTED]. Missing data (including those after use of rescue medication) will be handled by NRI method. The number, percentage of subjects achieving the goal and Clopper-Pearson exact 95% confidence intervals will be reported. The differences in proportion between treatment groups, along with p-values and the 95% CIs will also be reported. Weekly peak NRS ≥ 3 reduction will be assessed among the subset of subjects whose baseline peak NRS is ≥ 3 .

Sensitivity analyses will be performed in the PPS and TCS using observed data.

E. Exploratory Efficacy Outcome Analysis

Below exploratory endpoints will be analyzed in a similar manner as the secondary continuous variables with the MMRM model based on FAS using observed data.

- Change in DLQI from Baseline to Week 12.
- Change in POEM from Baseline to Week 12.
- Percent change in SCORAD total and individual symptom scores from Baseline to Week 12.

The primary and sensitivity analysis for all efficacy endpoints are summarized in **Table 3**.

Table 3 Summary of Efficacy Analyses

Efficacy Endpoint	Primary Analysis	Sensitivity Analysis
DB Treatment Period		
Primary		

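### Continuous itch and BSA are analysed on observed data with no rule for scores after rescue, and no planned analysis of them removes those scores

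*SAP*

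**What the plan says.** - **Objective (Protocol 2).** "To assess the efficacy of etrasimod monotherapy (1 or 2 mg) in subjects with moderate-to-severe AD during the Double-Blind Treatment Period".
- **Primary endpoint (SAP 8.B, same rule in Protocol 11.4.1).** "EASI scores after rescue medication use will be set to missing"; the gaps are then multiply imputed.
- **Responder endpoints in SAP 8.D** (peak NRS reduction of at least 3, EASI-50, EASI-90). "Missing data (including those after use of rescue medication) will be handled by NRI method". A subject with post-rescue data at Week 12 is therefore a non-responder.
- **Continuous itch and BSA (SAP 8.D).** Percent change in weekly peak NRS, and change and percent change in BSA, "measured at visits (weeks) up to Week 12 will be analyzed with a MMRM model based on FAS using observed data". Nothing in 8.D says what happens to their values after rescue. Table 3 lists the main analysis as FAS, OC (MMRM), and the two sensitivity analyses, in the PPS and the TCS, are also OC.
- **Meaning of observed case.** For the mFAS sensitivity analyses, SAP 8.B and 8.C gloss OC as "observed data regardless of rescue medication uses and without imputation". SAP 8.B repeats this for the PPS and TCS analyses of the primary endpoint.
- **Pointer in SAP 5.H.** Speaking of the FAS analyses of Week 12 efficacy, primary and secondary alike, it says that "the handling of missing data and rescue medication uses are specified in Section 8.B - 8.C". Section 8.D is not named.

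**The concern.** Scores taken after topical or systemic corticosteroid reflect etrasimod (or placebo) plus rescue, which is not what a monotherapy objective asks about. After systemic rescue, Protocol 6.8.2 also requires study treatment to stop, so some retained values may be off study drug.

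Itch and BSA are closely tied to rescue. Under Protocol 6.8.2, "rescue therapy will be permitted at the discretion of the investigator based on disease worsening as evaluated by the investigator", with increased BSA given as an example, or on the subject's report of worse itch. The same section asks for rescue to be withheld for the first 4 weeks where possible. If that is followed, post-rescue values fall mainly at later visits, including Week 12, where the endpoints are read.

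The same diary, subject and week can then be a failure in the responder analysis and an improvement in the continuous analysis, with no reason given for the difference. A reader who sees the two itch results diverge could not tell how much of the gap comes from rescue handling.

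**Working it through.** **Step 1. The rules side by side.**

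| Endpoint | Source | Analysis | Values after rescue |
|---|---|---|---|
| Percent change in EASI | SAP 8.B; Protocol 11.4.1 | ANCOVA, FAS, multiple imputation | Set to missing, imputed |
| EASI-75, vIGA response | SAP 8.C; Protocol 11.4.1 | CMH, FAS, NRI | Non-response |
| Peak NRS reduction of at least 3, EASI-50, EASI-90 | SAP 8.D | CMH, FAS, NRI | Non-response |
| Percent change in weekly peak NRS; change and percent change in BSA | SAP 8.D, Table 3 | MMRM, FAS, observed data | No rule stated; the OC label implies retained |
| Sensitivity analyses of the row above | SAP 8.D, Table 3 | MMRM, PPS and TCS, observed data | Same |

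The first three rows are the continuous and binary forms of one approach: scores after rescue earn no credit. The last two rows follow a different one. There are two approaches here.

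**Step 2. Does any other text supply the rule?** Protocol 11.4.1 announces handling for primary and secondary endpoints but gives rules only for EASI percent change and for dichotomous endpoints. SAP 5.H sends the reader to 8.B and 8.C, which say nothing specific to continuous itch or BSA. Protocol 11.5 specifies the MMRM for these endpoints and is silent on rescue. SAP 11, on changes from the protocol, does not mention the matter.

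**Step 3. Does any planned analysis remove post-rescue itch or BSA values?** The PPS and TCS restrict which subjects are included. They do not delete values after rescue, and both use observed data. The post hoc repeat of the itch MMRM in SAP 12.A uses the same 8.D model. On the OC reading the answer is no.

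**Step 4. Direction of the effect.** Let D be the between-group difference in improvement that would be seen without rescue, r the extra improvement that rescue gives a rescued subject (taken as equal across arms), and pP and pA the proportions of placebo and active subjects with retained post-rescue values at Week 12. Then approximately:

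observed difference = D − r × (pP − pA)

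None of r, pP and pA is in the documents. The values below are assumed, only to show the sign, with r from 20 to 40 percentage points:

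- pP = 10%, pA = 10%: shift = r × 0 = 0.
- pP = 20%, pA = 10%: 20 × 0.10 = 2 to 40 × 0.10 = 4 points towards zero.
- pP = 40%, pA = 10%: 20 × 0.30 = 6 to 40 × 0.30 = 12 points towards zero.
- pP = 10%, pA = 30%: 20 × 0.20 = 4 to 40 × 0.20 = 8 points away from zero.

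**Step 5. The plan's own figure.** The only sample-size figure is for EASI: difference 35, SD 41, one-sided 0.025. A two-sample t-test with 30 evaluable per arm gives 90.2% power, and 30 / (1 − 0.25) = 40 per arm, as stated. This point leaves that figure unchanged.

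**The case against.** The strongest reply is that the text is ambiguous. The itch and BSA sentence in 8.D omits the regardless-of-rescue qualifier, and the key to Table 3 expands OC only as observed case. SAP 5.H could be read as carrying the 8.B rule across, and the dichotomous paragraph of 8.D counts post-rescue data among missing data. On that usage, observed data might already exclude post-rescue values. This stands in part: the SAP does not say outright that these values are kept. But each time the SAP explains observed case in words, the meaning is regardless of rescue, and Table 3 applies that label here. A programmer following the plan would keep them. If the intention was to exclude them, the same wording change is needed.

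Keeping post-rescue data is also a legitimate treatment-policy strategy. That stands. The weakness is that the strategy is neither stated nor justified, and has no companion analysis under the primary's rule.

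Stronger readings that a reader might infer, and that the documents do not support:

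- **That the SAP contradicts the protocol.** Protocol 11.4.1 applies its set-to-missing rule to EASI only, and Protocol 11.5 gives the MMRM without a rescue rule.
- **That the treatment effect is diluted.** More rescue on placebo is plausible, because rescue follows worsening, but no rescue rates are given.
- **That a power loss can be computed from 35 and 41.** Those belong to EASI. No effect size, SD or power is stated for itch or BSA, and SAP 5.F reports even the primary and key secondary comparisons in an exploratory manner.
- **That deleting post-rescue values would make the two itch endpoints estimate the same thing.** The responder analysis is limited to subjects with baseline peak NRS of at least 3 and uses NRI, so they would still differ.

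**Conclusion.** The point holds as a gap in the plan. Read with its own gloss of observed case, the SAP analyses continuous itch and BSA with post-rescue values included, gives no reason for departing from the approach used for EASI and for itch response, and plans no analysis of these outcomes without them. This sits poorly with a monotherapy objective and with the pointer in SAP 5.H.

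The size is unknown. Attenuation is the expected direction if rescue is more frequent on placebo; the shift is zero at equal rates and reverses if active subjects are rescued more. The conclusion rests on reading observed data in 8.D through the OC label and its gloss elsewhere. Severity is minor to moderate.

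**What to change.** In SAP 8.D, state the rescue strategy for the continuous secondary endpoints. Set itch and BSA values after first rescue use to missing before fitting the MMRM, with the same definition of rescue as the primary analysis in 8.B. For the diary, apply this to daily entries before weekly averaging, so that the existing minimum of 3 entries decides whether a week counts. In Table 3, list the regardless-of-rescue MMRM beside it as a sensitivity analysis, and add 8.D to the pointer in 5.H.

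This SAP already contains post hoc analyses defined by treatment group (Section 12), so unblinding may have taken place. If it has, add the new analysis as a labelled ad hoc analysis, as SAP Section 1 allows, and leave the planned one in place.

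Extending the rule to the exploratory DLQI, POEM and SCORAD models is optional. The sentence in 5.H covers only primary and secondary endpoints.

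The cost is a few sentences and one data step. The downside is fewer observed values and reliance on missing-at-random after rescue, which the primary analysis already accepts. Reporting both versions loses no information.
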